Surgical outcome will also be assessed via: 1) patient-oriented outcome scores^{59,76}, 2) AP laxity (an indicator of graft integrity^{6,44} and knee kinematics²³), 3) isokinetic strength (an indicator of dynamic knee function¹⁶), and 4) clinical outcome scores^{48,78}. Analysis of primary and secondary outcomes will enable us to determine the long-term effects of initial graft tension on cartilage status and knee joint function, and to evaluate the relationships between the longitudinal changes that occur in TF joint space narrowing (x-ray), cartilage thickness (MRI), general MRI scores (WORM score), knee laxity (KT-1000), thigh strength (Biodex strength test, 1 legged hop test) and patient-oriented outcome scores (SF-36, Knee Osteoarthritis Outcome Score). In the past funding cycle, data were obtained prospectively from ACLR patients and matched control subjects from the time of recruitment (pre-operative) through 84 months of healing. In this update, additional evaluations will be performed 144 and 180 months, a time frame in which cartilage damage should become more pronounced in this patient population. These analyses will shed light on potential factors that may play a role in the degenerative process and long-term outcome.

2. Subjects

108 ACL-injured patients, who required ACLR, were recruited during the first three years of the initial funding cycle. It was our intent to identify patients with isolated ACL injuries while minimizing confounding variables. To do this, all patients who came through the sports medicine clinics of University Orthopaedics Inc between 02/09/2004 and 02/08/2007 were considered for the study. All who met the pre-operative inclusion criteria and did not meet the exclusion criteria (Table 1) were asked to participate and provide their informed consent. Additional “intra-operative” inclusion/exclusion criteria were then evaluated at the time of surgery (Table 1). If the patient remained eligible, minimum likelihood allocation was used to randomly assign each subject to one of the two initial graft tension groups¹. Randomization was performed to achieve balance between the treatment groups for characteristics that would influence long-term outcome and cartilage health; age, gender, race, and activity level (Tegner score). The number of patients who injured their ACL and choose ACLR within the clinical practice was documented, and the reasons for excluding subjects were recorded.

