60 “matched” control subjects, who had no known history of knee injury or symptoms of arthritis, were recruited from the hospital campus, local colleges, and Providence community. They were selected to match the frequency of individuals by age (± 5 years), gender, race, and activity level (Tegner score ± 1 point). The subjects’ knees were evaluated by clinical exam at a screening visit. Subjects were not included in the control group if they have a side-to-side difference in AP laxity greater than or equal to 2-mm (KT-1000), a Tegner activity score less than 5⁶⁹, or if they meet any of the other exclusion criteria (Table 1). It was our intent to establish a control group that matched the characteristics of the population at risk to ACL injury.

3. Research Design

This study is designed as a prospective, randomized, double-blinded controlled trial comparing the outcome of two different initial tension conditions applied to the ACL graft at the time of surgery, and to determine the relationship between factors that may predict who will be risk for OA. The project statistician and the operating surgeon initially knew a patient’s assignment at the time of surgery, however, the

surgeon was not allowed to review the assignment once the surgery was completed, and the statistician was not allowed to review the assignments until after all the subjects were enrolled. The patient, the therapist performing the follow-up assessments, the AP laxity and isokinetic strength testing, the engineer performing the radiographic joint space width and cartilage thickness measurements, and the radiologist performing the WORM scoring will continue to be blinded from the subject's group assignment throughout the study. An intent-to-treat protocol is being utilized. All subjects randomized to each group are being followed, and all available data will be analyzed even if the graft fails, if the subject is unwilling to perform a particular follow-up test (missing data), or if a subject completely drops out of the study.

Table 1. Inclusion/exclusion criteria for patient enrollment.

Treatment Groups (Hi- and Lo-tension)	
Inclusion Criteria	Male or female subjects between the ages of 15 and 50 years with unilateral ACL injury.
	Candidates for ACLR using bone-PT-bone or four-stranded hamstring tendon autograft.
	A Tegner activity score ⁶⁹ ≥ 2 .
	Minor tears of the menisci that require minimal treatment (<1/3).

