Exclusion Criteria	An ACL tear occurring more than 12-months prior to the 1st office visit.
	Previous injury to either knee.
	Increased clinical laxity of the MCL, LCL, or PCL as compared to the control knee.
	Evidence of degenerative arthritis on radiographs.
	Women who are pregnant.
	Diseases that predispose a patient to articular cartilage damage.
	Moderate sized fissures or lesions in articular cartilage.
	Meniscal tears requiring partial meniscectomy involving more than 1/3 of meniscus.
Control Group	
Inclusion Criteria	Male or female subjects between the ages of 18 and 50 years.
	A Tegner activity score ⁶⁹ ≥ 2 .
Exclusion Criteria	Previous injury to either knee.
	Increased laxity of the MCL, LCL, or PCL compared to the control knee.
	Evidence of degenerative arthritis on radiographs
	Women who are pregnant.
	Diseases that predispose a patient to articular cartilage damage (e.g. rheumatoid arthritis, osteoporosis, metabolic diseases).

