The intra-articular position of the graft has been shown to affect the graft forces post-operatively, and was standardized in this study^{10,17,25,38,46}. A 2 mm deviation in femoral graft placement has been shown to have a pronounced effect on the graft elongation pattern⁴⁵. A graft that is placed to far anterior on the femur will cause it to get tight in flexion and slack in extension. Likewise, a graft that is placed in the "over-the-top" position will get tight in extension and slack in flexion. Thus, intra-articular graft position may influence the healing response^{9,70}. However, all the surgeons utilized the same drill guide system and anatomical landmarks to standardize graft position across subjects. Although variation may still exist, we have previously shown that they are equally distributed within each treatment group⁹.

Another standardized variable, which could possibly affect outcome, is the rehabilitation program prescribed following surgery⁸. Recent data comparing commonly used rehabilitation protocols suggest otherwise. We have shown that rehabilitation with either an "accelerated" or "non-accelerated" program produces the same outcome with respect to AP knee laxity, clinical assessment, patient satisfaction, functional performance, strength, and proprioception^{5,8}. In the current study, all subjects were required to follow the "accelerated" rehabilitation program. They received supervised post-operative physical therapy for a minimum of 16 weeks. Because the patients were randomly assigned to each treatment group, we feel that any deviation from the rehabilitation program (either produced by the patient's inability to keep up with the program, or the patient's unwillingness to follow the prescribed rehabilitation) was equally distributed between the two groups.

7. Protocol Summary

When a subject (either surgical or control) consents to continue their participation in the study, 144- and 180-month follow-up assessments will be performed. All patients have been previously enrolled into the study. However, the lay summary consent forms were based on an 84-month follow-up. Therefore, the subjects will need to be re-consented in order to participate in the extended study. The clinical coordinator will consent the patients after contacting them via mail with a phone call follow-up. Within the initial contact letter, a card will be provided so that the subject can let us know if they do not want us to contact them by phone.

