Treatment Comparisons - Primary Outcome Measure: Repeated measures analysis of variance will be used to evaluate differences among treatment groups with respect to temporal changes in joint space width (i.e. joint space narrowing). The statistical model will include fixed factors representing treatment group (“low-tension”, “high-tension” and “control”), limb (operative vs. contra-lateral or two controls), location (medial vs. lateral), time (baseline, 12-, 36-, 60-, and 84-month), and their interactions. If significant interactions are detected, simple effects will be compared using the Student-Newman-Keuls procedure based on the appropriate error terms⁸⁰. Because one of the repeated factors (i.e. time) is quantitative, orthogonal polynomial will be used to partition the time effect into its individual quantitative components (i.e. linear and quadratic). The significance of these orthogonal contrasts will be used to evaluate the linearity (or non-linearity) of the temporal trend associated with degeneration. Analyses will be performed using SAS, PROC MIXED⁵² that allows for covariance structures other than compound symmetry (e.g. unstructured, autoregressive, spatial power law). It is expected that the variability across subjects may increase across time due to only a subset of individuals exhibiting degeneration, which would violate the standard homogeneity of variance assumptions. The normality assumption will be examined based on residuals using normal probability plots and the Wilk-Shapiro test. If necessary, data will be transformed prior to analysis in order to satisfy the distributional assumptions.

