Missing Visits and Subject Loss to Follow-up: Unlike traditional software used for repeated measures analyses (e.g. SAS PROC GLM and BMDP -2V), PROC MIXED appropriately handles incomplete data due to missed visits without completely excluding subjects from the analysis. The pattern of missing data is assumed to be random, which in-practice, is likely to be violated to some degree. We will test for differences in the rate of missed visits across treatment groups and across time using categorical repeated measures (SAS, PROC CATMOD). The proportion of subjects that are loss to follow-up will be compared across treatment and control arms using a chi square test. Though we are finding that missed visits are infrequent and most likely equally distributed across treatment groups, we will examine whether specific baseline characteristics that may be predictive of outcome are also associated with missed visits using logistic regression. We recruited 54 subjects per group in an effort to have 46 assessable subjects per group at the three-year follow-up visit based on the estimated 15% dropout rate. We have more than met this goal (3% drop out in our treatment groups and 15% drop out in our control group at 3 years. For the proposed 180-month follow-up, we expect that we will have at least 35 patients/subjects in each group (20% drop out rate of subjects currently enrolled).

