Justification of Sample Size based on Primary Outcome Measure: The estimated sample size of 35 assessable subjects per group through the 84-month study period will result in having sufficient power ($1-\beta=0.80$ using $\alpha=.05$) to detect a mean difference between groups of 0.25 mm in joint space narrowing over the 84-month study period. This estimated difference is based on the following rationale. Previous studies have shown that patients with primary OA exhibit an estimated 0.3-mm change in joint space width per year^{51,63}. Since we will be studying patients at the time of OA onset, we will assume that patients who undergo initial changes will exhibit an average joint space narrowing of 0.1 mm per year, or a total of approximately 0.6 mm over the 84 months. This estimate was conservatively adjusted based on the study by Johma et al, who found that only 50% of the subjects that undergo ACL reconstruction after injury exhibit early degenerative changes following surgery⁵⁰. After taking into account that only a subset of subjects randomized may exhibit OA, the resulting mean difference is decreased to be 0.25-0.30 mm over the 84-month study period. An additional consequence of only a subset of the patients that are randomized exhibiting degeneration is an increase in the variability encountered across subjects with respect to joint space narrowing. The variability estimate used in our computations ($\sigma_{\Delta}=0.35$ mm) resulted from increasing the estimate derived from the literature for a group of subjects with OA in order to reflect our expected mixture of two subsets of subjects. Based on each subset having $\sigma_{\Delta}=0.20$, with 50% of the patients exhibiting narrowing a total of 0.6 mm and 50% showing no degeneration, the resulting overall estimated $\sigma_{\Delta}=0.35$. Assuming joint space width at baseline is approximately 4.5 mm³⁰, this detectable mean difference (0.25 mm) represents an approximate 5% change between the treatment groups in the mean rate of degeneration. We recruited 54 subjects per group in an effort to have 46 assessable subjects per group at the three-year follow-up visit based on the estimated 15% dropout rate^{4,7}. We have more than met this goal (3% drop out in our treatment groups and 15% drop out in our control group at 3 years). For the proposed 180-month follow-up we expect that we will have at least 35 patients/subjects in each group (20% drop out rate of subjects currently enrolled).

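### No planned analysis adjusts the contrasts with non-randomised controls for age, gender, race or Tegner score, and the plan does not say which contrast decides the primary hypothesis

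*Combined protocol and SAP*

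**What the plan says.** Section 2 (Subjects) explains the allocation of the two tension groups: "Randomization was performed to achieve balance between the treatment groups for characteristics that would influence long-term outcome and cartilage health; age, gender, race" and, completing the list, Tegner activity level. Controls came from the hospital campus, local colleges and the community, and were "selected to match the frequency of individuals by age (± 5 years), gender, race, and activity level", the last within 1 Tegner point.

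The primary hypothesis (Specific Aims; section 1) has two parts, and each compares a tension group with controls: high tension equal to control, low tension less than control, in joint space width at 15 years.

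Section 8 (Primary Outcome Measure) models temporal change in width with fixed factors for treatment group, limb, "location (medial vs. lateral), time (baseline, 12-, 36-, 60-, and 84-month), and their interactions". Simple effects are compared by Student-Newman-Keuls if interactions are significant. Age and gender appear as possible factors only in the model relating laxity to OA progression, which uses the experimental subjects and not the controls.

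On loss, section 8 reports "3% drop out in our treatment groups and 15% drop out in our control group at 3 years" and says "we will examine whether specific baseline characteristics that may be predictive of outcome are also associated with missed visits using logistic regression". The result of that regression has no stated role in the primary model. For the extension, section 7 says "the subjects will need to be re-consented in order to participate in the extended study".

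**The concern.** The protocol itself treats the four factors as prognostic. Randomisation protects the comparison of high with low tension, but it does not protect the comparison of either group with controls, and that is where the hypothesis sits. Matching was done once, at entry, with tolerances. Loss at 3 years was already unequal, everyone must consent again, and the plan expects as few as 35 per group from 54 patients per arm and from 54 or 60 controls (Specific Aims and section 2 give both figures). Any imbalance left by matching or created by loss, in a factor that affects narrowing, biases the contrast with controls and could create or hide a difference.

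How much depends on the contrast. The hypothesis is worded as width at 15 years, whereas the analysis is worded as change over time, with simple effects also available. The plan does not say which one is decisive.

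**Working it through.** **The plan's own figure.** The sample-size paragraph of section 8 starts from "The estimated sample size of 35 assessable subjects per group through the 84-month study period", a difference of 0.25 mm, SD of change 0.35 mm, alpha 0.05 (taken as two-sided) and power 0.80.
- SE = 0.35 × √(2/35) = 0.0837 mm. Power = Φ(0.25/0.0837 − 1.96) = 0.848, or 0.838 by the t distribution.
- The plan's mixture gives an unrounded SD of √(0.20² + 0.25 × 0.6²) = 0.3606 mm, and power 0.827, or 0.816 by t.

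The stated 0.80 is therefore met. The calculation has no covariate term and neither supports nor refutes the concern. These are 84-month inputs; no 180-month values are given.

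**Bias in an unadjusted contrast of index-knee change.** Let r be the correlation of a factor with narrowing and d the imbalance in SD units. The documents give neither, so both are assumed. Bias = r × d × 0.35; type I error = Φ(−1.96 + bias/SE) + Φ(−1.96 − bias/SE).

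| r | d | Bias (mm) | Type I error |
|---|---|---|---|
| 0.1 | 0.10 | 0.0035 | 0.050 |
| 0.2 | 0.25 | 0.0175 | 0.055 |
| 0.3 | 0.50 | 0.0525 | 0.096 |

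The last row is an upper case. For age, 0.5 SD would need the 5-year tolerance used entirely in one direction: 5/(35/√12) = 0.49 SD if ages were uniform on 15–50.

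**Which contrast is exposed.** A null simulation used 35 per group and d = 0.5. It assumed a factor that shifts width by 0.3 mm and narrowing by 0.1 mm per SD in both knees, a between-subject SD of 0.6 mm and a measurement SD of 0.25 mm. Rejection rates were 19% for width at follow-up, 9% for change from baseline and 5% for side-to-side change. If the factor affects level only, they were 14%, 5% and 5%.

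For width at 180 months, with an assumed SD of 0.5–1.0 mm and r now the correlation with width, r × d × SD gives 0.005–0.010, 0.025–0.050 and 0.075–0.150 mm in the three rows above.

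**Loss to follow-up.** The largest shift of a retained mean when a fraction p is lost is φ(z)/(1 − p), with z = Φ⁻¹(1 − p). This is multiplied by the latent correlation between loss and the factor.
- Controls, 60 to 35: p = 0.417, shift 0.67 SD. Patients, 54 to 35: p = 0.352, shift 0.57 SD.
- Selective loss in controls only, latent correlation 0.3: 0.67 × 0.3 = 0.20 SD; at r = 0.3 the bias is 0.20 × 0.3 × 0.35 = 0.021 mm, type I error 0.057.
- Same mechanism in both groups: (0.67 − 0.57) × 0.3 = 0.03 SD; bias 0.03 × 0.3 × 0.35 = 0.003 mm, type I error 0.050.
- The observed 3-year loss (p = 0.03 and 0.15, shifts 0.07 and 0.27 SD), same mechanism: (0.27 − 0.07) × 0.3 = 0.06 SD; bias 0.006 mm, type I error 0.051.

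**High versus low.** In simulation, 108 patients were allocated by marginal minimisation (a stand-in for minimum likelihood allocation), followed by random loss to 35 per arm. With assumed R² of 5/10/20/30%, the unadjusted test had alpha 0.048/0.042/0.038/0.035. Power for 0.25 mm was 0.84/0.85/0.85/0.86 unadjusted and 0.85/0.86/0.90/0.93 adjusted.

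**Form of the adjustment.** If a factor acts in patients only and the target is the patient mean, simulated bias was −0.001 mm unadjusted, −0.027 mm with a common slope and −0.001 mm with group-specific slopes.

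**The case against.** The strongest reply is that the planned model already does much of the work. Baseline is a level of time and the other knee is a level of limb, so group-by-time removes stable differences in width, and group-by-limb-by-time removes effects shared by both knees. This stands. A reader might infer that the control contrasts rest on matching at entry alone; that is true only of width at one visit and of single-knee simple effects.

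The attrition case is also weaker than it looks. A large shift needs selective loss in controls and random loss in patients, and nothing in the documents supports that asymmetry. The mixed model uses all available data: with loss after 84 months and an assumed correlation of 0.5 or 0.7 between 84- and 180-month change, a simulated bias of 0.020 mm fell to 0.010 or 0.006 mm. This stands too.

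Adjustment has risks of its own. A common slope can add bias, and choosing slopes after a test at about 35 per group would let the data select the model. Both bear on how to adjust, and the fix takes account of them.

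It may also be said that the allocation sentence concerns the randomised arms only. That is so. It is used here to show that the plan regards the factors as prognostic; the matching paragraph and the primary model carry the rest.

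**Conclusion.** The concern holds in limited form. The omission is plain in the text: no analysis in section 8 adjusts the contrasts with controls, and the deciding contrast is not named. The size of any bias cannot be derived from the documents. It is probably small: 0.018 mm on middling assumptions, 0.053 mm in an upper case, about 0.003 mm if loss is selective in the same way in both groups, and negligible if matching held. It would be largest if width at 15 years decides the hypothesis.

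Three stronger inferences are not supported:
- **The high-low estimate is biased.** It is not: allocation balanced these factors, and adjustment would only add a little precision.
- **The age limits broke the matching.** Patients could be 15 to 50, and Table 1 admits as controls "Male or female subjects between the ages of 18 and 50 years". The gap at 15–17 lies within the 5-year tolerance.
- **Some patients had no eligible control on activity.** Section 2 excludes controls with a Tegner score below 5, whereas Table 1 admits 2 or above. Under the section 2 limit a patient scoring 2 or 3 would have no control within 1 point, but the documents do not show that any such patient was enrolled. The two limits must be reconciled in any case.

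This is a change that should be made because it is cheap and the data exist, and not because the trial's conclusions are shown to be at risk.

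**What to change.** Make the change in the same dated revision that extends the model's time factor to 144 and 180 months, before those data are analysed.

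1. Name the index-knee contrast with controls that decides the hypothesis (width at 15 years or change), and state whether the control comparator is one assigned knee or the mean of two.
2. In that analysis add baseline age, gender, race (collapsed if sparse) and Tegner score, each with its interaction with linear time. Allow the slopes in advance to differ between patients and controls, and estimate the contrast at the patient covariate mean. Do not choose the slopes after a test.
3. Report the unadjusted section 8 model alongside, with a table of baseline balance among those assessed at 180 months.
4. Leave the published 7-year analysis unchanged.
5. Separately, reconcile the two Tegner limits for controls.

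Cost: with race in two categories, 4 main effects and 4 interactions with linear time make 8 degrees of freedom, and 8 × 2 = 16 with separate slopes for patients and controls; with three race categories, 10 × 2 = 20. About 3 × 35 = 105 subjects are expected. The change is a documented departure from the 7-year model. It needs no new data, because the four factors were used for allocation and matching.

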Patients were included in the study if they were candidates for autogenous ACLR with either a bone-patellar tendon-bone or a 4-stranded hamstring tendon graft. Due to the popularity of these graft types, both were included to extend the recruitment base. It should be noted that we initially proposed to include only bone-patellar tendon-bone grafts in the study. However, the recent surge in popularity of the hamstring tendon graft and the need to extend our recruitment based convinced us to include this procedure after eight months of recruiting candidates for patellar tendon autograft only. This was justified since recent biomechanical studies have shown that the structural properties of the patellar tendon autograft are equal to that of the 4-stranded hamstring tendon autograft ⁷⁹. Likewise, the in-situ forces, the passive load-displacement response, and dynamic kinematics of reconstructed knees with patellar tendon and 4-stranded hamstring tendon grafts are equivalent ^{68,82}. Recent prospective randomized clinical trials comparing these two graft types have shown that functional and patient-oriented outcomes are equivalent ^{2,3,19,33,34,41,42,49,62,64}. Finally, the two graft tension procedures in this study produced the same AP laxity values between graft types. Other than graft type, all surgically related parameters were standardized across surgeons. The same surgical instrumentation within each graft type was used to ensure that intra-articular graft placement was similar between patients. "Aperture" fixation interference screws were used to standardize graft fixation. Another variable, which could possibly affect outcome, is the rehabilitation program prescribed following surgery ⁸. Recent data comparing commonly used rehabilitation protocols has shown that rehabilitation with either an "accelerated" or "non-accelerated" program would produce the same clinical, functional and patient oriented outcomes ^{5,8}. Nonetheless, all

subjects were required to follow the same “accelerated” rehabilitation program, which was geared to get patients back to sport within 6-months.

4. Independent variable (Initial graft tension condition based on AP laxity)

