5.5. Clinical outcome

Clinical outcome will be assessed using the International Knee Documentation Committee (IKDC) knee rating scale^{23,48}. The IKDC rating has been validated for ACLR⁴⁸. The IKDC scores evaluate four categories: 1) the patient's subjective assessment of function, 2) symptoms, 3) range of knee motion, and 4) clinical examination. The IKDC score rates knees as normal, nearly normal, abnormal, and severely abnormal, which can be transformed to an ordinal scale of 1 (normal) to 4 (severely abnormal). The final IKDC rating is then based on the score of the worst category⁴⁸. In addition, height, weight, body mass index, thigh circumference (6cm above joint line) and the number of recurrent injury episodes is recorded. A sports medicine physician and a physical therapist will continue to independently perform all of the pre- and post-operative clinical examinations.

6. Controlled Variables

Investigators have shown that the initial graft tension level required to restore normal knee laxity is specific to the graft material, cross-sectional area of the graft, and the free length of the graft between fixation sites¹⁵, and these were controlled in this study. Initially, subjects undergoing ACL reconstruction using a bone-patellar tendon-bone autograft were recruited to control the variability due to graft type. However, there has been a recent surge in the popularity of the 4-stranded hamstring tendon graft. Thus, we elected to recruit patients who were candidates for ACL reconstruction with 4-stranded hamstring autografts to increase our population base. This was justified because recent biomechanical studies have demonstrated that the structural properties of the patellar tendon autograft are equal to that of the 4-stranded hamstring tendon autograft⁷⁹. Likewise, the in-situ forces, the passive load-displacement response, and dynamic kinematics of reconstructed knees with patellar tendon and 4-stranded hamstring tendon grafts are similar^{68,82}. Finally, recent prospective randomized clinical trials have shown that functional outcome following ACL reconstruction with 4-stranded hamstring or patellar tendon autografts are equivalent^{2,3,19,33,34,41,42,49,57,62,64}.

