Treatment Comparisons - Secondary Outcome Measures: Repeated measures analyses of variance will also be used to test for differences in secondary outcome measures corresponding to knee kinematics, dynamic function, patient reported outcomes, and clinical outcomes. For measures that are performed on each limb (e.g. A-P laxity), the statistical model will include fixed factors representing treatment group, limb, and time, along with their interactions. Repeated measures analyses on secondary outcome that are not limb-specific (e.g. KOOS and SF36) will include only treatment, time, and their interaction as factors. Post hoc analyses involving tests of simple effects and orthogonal polynomials will be similar to methodology previously described for joint space width. Because specific secondary outcome measures are assessed more frequently in the two experimental arms than in the control group (Tables 2&3), direct post hoc comparisons involving the two tension groups and examination of temporal trend in these group will utilize the additional assessments.

Relationship between A-P Laxity and Progression of OA: The longitudinal relationship between A-P laxity and progression of OA as measured by joint space narrowing (both radiographically and using MRI) will be examined in the context of hierarchical linear modeling¹³, also known as random coefficient modeling. Using data obtained from the experimental subjects, SAS PROC MIXED will be employed to examine the association between individual subjects' changes in A-P laxity with their changes in joint space width (radiography) or cartilage thickness (MRI). This will be accomplished by considering A-P laxity as a covariate (predictor) that would potentially change over time with joint space width and cartilage thickness being considered as the dependent measures. Individual subjects are modeled based on unique intercepts and slopes corresponding to time and the covariate. Across subject factors such as tension group, gender, graft type, and age will also be considered. A similar analysis will be performed to establish the relationship between isokinetic strength, KOOS, functional testing and OA progression.

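### Graft type varied once eligibility was widened, but it was not balanced at allocation and is missing from the primary joint-space model

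*Combined protocol and SAP*

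**What the plan says.** **Eligibility.** Section 3 records that only patellar tendon grafts were first proposed, and that popularity and recruitment "convinced us to include this procedure after eight months of recruiting candidates for patellar tendon autograft only". Table 1 now admits "Candidates for ACLR using bone-PT-bone or four-stranded hamstring tendon autograft". Patients seen "between 02/09/2004 and 02/08/2007 were considered for the study" (section 2), a 36-month window.

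**Allocation.** Section 2 says that "minimum likelihood allocation was used to randomly assign each subject to one of the two initial graft tension groups", aiming for "balance between the treatment groups for characteristics that would influence long-term outcome and cartilage health; age, gender, race, and activity level (Tegner score"). Graft type is not listed.

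**Primary model.** Section 8 (Treatment Comparisons - Primary Outcome Measure) has treatment group, "limb (operative vs. contra-lateral or two controls), location (medial vs. lateral), time (baseline, 12-, 36-, 60-, and 84-month), and their interactions". There is no graft term.

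**Secondary model.** Section 8 (Relationship between A-P Laxity and Progression of OA) models joint space width or cartilage thickness in the surgical patients, with laxity as a time-varying covariate: "Across subject factors such as tension group, gender, graft type, and age will also be considered".

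**Control of graft material.** Section 6 says that the tension needed to restore laxity depends on graft material, cross-section and free length, "and these were controlled in this study". The same paragraph then describes giving up the restriction to one graft. Section 3 lists graft type as the exception to surgical standardisation.

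**The concern.** Restricting the trial to one graft was the original means of control. When that was dropped, neither the allocation nor the primary analysis took its place, although section 6 still claims control and section 8 treats graft type as a possible predictor of joint space elsewhere.

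The evidence offered for pooling concerns structural properties, graft forces, load-displacement, kinematics, and functional and patient-oriented outcomes. None of it is stated to concern joint space or OA, which is the primary outcome.

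Three things are at stake. Between-graft variation stays in the error term. A chance difference in graft mix between the tension arms goes unadjusted. The report would not show whether the tension effect looks similar in the two grafts.

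**Working it through.** **Inputs from the documents.** 108 patients randomised, 54 per tension arm (Specific Aims; section 2). From section 8, Justification of Sample Size: 35 assessable per group, power 0.80, alpha 0.05, planning difference 0.25 mm over 84 months, SD of change 0.35 mm. Sidedness is not stated; two-sided is assumed.

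**Assumptions, not in the documents.** Hamstring share p = 20–50%; graft effect on narrowing g = 0.1–0.3 mm; graft type independent of arm, as under simple randomisation. The imbalance formula is symmetric in p, so 20–50% also covers 50–80%.

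**1. The plan's own figure.** The mixture SD is √(0.20² + 0.25 × 0.6²) = √0.13 = 0.361, printed as 0.35. With n = 2(1.960 + 0.842)² × SD² / 0.25²:
- SD 0.361 gives n = 33 per group (34 by t-test); t-test power at 35 is 0.816.
- SD 0.35 gives n = 31 (32 by t-test); power at 35 is 0.848 (0.838 by t-test).

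The stated 35 per group is reproduced with the unrounded SD and is slightly conservative with the printed one. Leaving out graft type does not undermine it.

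**2. Chance imbalance.** SD of the between-arm difference in hamstring share = √(2p(1−p)/n).

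| n per arm | SD, p = 0.20 | SD, p = 0.50 | P(≥10 points) | P(≥20 points) |
|---|---|---|---|---|
| 54 | √(0.32/54) = 7.7 points | √(0.50/54) = 9.6 points | 18–29% | 1–4% |
| 35 | √(0.32/35) = 9.6 points | √(0.50/35) = 12.0 points | 29–40% | 5–12% |

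At 54 per arm and p = 0.50, the median absolute imbalance is about 0.674 × 9.6 = 6.5 points.

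**3. Shift in high versus low.** Shift = g × imbalance. The range runs from 0.1 × 0.10 = 0.01 mm to 0.3 × 0.20 = 0.06 mm, which is 4–24% of 0.25 mm.

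**4. Precision.** Residual variance after adjustment = 0.35² − p(1−p)g².
- p = 0.20, g = 0.1: 0.1225 − 0.0016 = 0.1209, SD 0.348, power at 35 of 0.853.
- p = 0.50, g = 0.3: 0.1225 − 0.0225 = 0.1000, SD 0.316, power at 35 of 0.911.

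Against 0.848 unadjusted, the gain is about 0.5 to 6 points of power.

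**5. Tension-by-graft interaction at 35 per arm.** SE = 0.35 × √(2[1/(35p) + 1/(35(1−p))]).
- p = 0.50: SE 0.167 mm, detectable interaction 2.80 × 0.167 = 0.47 mm, power for 0.25 mm 32%.
- p = 0.20: SE 0.209 mm, detectable 0.59 mm, power 22%.

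**The case against.** **No bias.** A reader might infer that widening eligibility partway, with graft type tied to calendar time, biases the high-versus-low contrast. The documents do not support that. Assignment was randomised, and both arms enrolled concurrently before and after the change. The contrast is unbiased in expectation, and its ordinary standard error already allows for chance imbalance. This stands.

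**Size.** A reader might also take an extreme case as typical. With a 50% share, a 95%-limit imbalance of 19 points (1.96 × 9.6) and an effect of 0.2–0.4 mm, the shift is 0.04–0.08 mm, or 15–30% of 0.25 mm. The median imbalance of 6.5 points with the same effects gives 0.013–0.026 mm. An effect of 0.4 mm would also exceed the mean narrowing the plan expects in reconstructed knees (50% × 0.6 = 0.30 mm). This stands too.

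**Laxity-based tensioning.** Tension was adjusted in each knee to a laxity target (section 4), which addresses the dependence of tension on graft material. Section 3 reports that achieved laxity was the same in both grafts, without figures. This answers part of the point. However, laxity was the target, held to ±1.0 mm, so similar values are expected by design. By section 6 the tension needed to reach it varies with graft material, and the Specific Aims place the effect on cartilage in tension and contact stress. Equal laxity does not establish equal joint-space outcome.

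**Graft type is already foreseen.** The secondary model does name it, for a joint-space outcome. But the factors are only to be considered, and the model conditions on laxity measured after surgery. It is not a graft-adjusted estimate of the tension effect.

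**Timing.** Recruitment closed in 2007 and the 7-year results are published, so allocation cannot be changed and any new covariate is a late addition. This determines the form of the fix.

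**Conclusion.** The point holds as a gap in adjustment and reporting, of moderate to minor weight. Graft type varied, was not an allocation factor, and is absent from the primary model. The claim in section 6 that graft material was controlled conflicts with section 3, which excepts graft type from standardisation.

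Under the assumed shares and effects, adjustment would gain about 0.5–6 points of power, and an imbalance of 10–20 points would move the contrast by 0.01–0.06 mm. The actual share and effect could lie outside these ranges; only the trial's data can say. Allocation balanced on age, gender, race and activity, so if graft choice follows those factors the real imbalance would tend to be smaller.

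Two further inferences are not supported: that the sample size is invalid (it reproduces), and that an interaction test would settle whether the conclusion applies to both grafts (power for 0.25 mm is only 22–32%).

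**What to change.** Before the 144/180-month analysis:

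1. **Prespecify a graft-adjusted version of the primary analysis**, labelled as added after the 7-year results. The primary model holds both limbs and only the operative one carries a graft, so a graft term with time alone would give both knees the same graft effect. Either nest graft type within the two reconstruction groups with its limb and time interactions, or compare high with low tension in a model of operative limbs in reconstructed patients only.
2. **State the graft mix for the comparison with controls**, who have no graft; the pooled mix across the two reconstruction groups is one choice.
3. **Report graft type by arm**, among those randomised and those analysed.
4. **Report the tension-by-graft estimate with a confidence interval, as descriptive only.**
5. **Reword section 6** to say that graft material varied, that tension was set by the laxity target, and that graft type is adjusted for.

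The cost is a few degrees of freedom, some SAP wording, and an analysis that must be presented as a late addition. The documents do not say whether any 144-month data have been analysed; if they have, the label should say so.
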